7.4.1. Primary Efficacy Variable

Since it is also possible to test for non-inferiority if the superiority hypothesis is not met, additional conditions are specified (see list below) to meet the strict requirements of a non-inferiority study, making it feasible to test for non-inferiority using the results from the superiority analysis, without a further separate analysis. The 90% confidence interval for the difference between the treatments

obtained from the superiority analysis gives the necessary information. Position of the lower end of the confidence interval relative to a pre-defined agreed 0.20 non-inferiority margin (Δ) provides the key information for making decisions (conclusions) about non-inferiority.

The additional conditions specified to make testing for non-inferiority feasible are the following:

- Pre-defined non-inferiority margin (Δ =0.20) based on both clinical and statistical considerations, i.e., chosen on the basis of external information and not chosen to fit the data.
- Analysis of the FAS and the PPAS, giving similar results with respect to p-values and confidence intervals for the efficacy measure at issue.
- Study design and implementation directed at minimizing deviation from protocol (a particularly important source of bias in non-inferiority studies), e.g., special care to minimize violations of: entry criteria; non-compliance; withdrawals; loss; missing data; etc. This should help ensure the second bullet point.
- Evidence that the standard treatment is showing its usual (expected) level of efficacy.

These specifications are in accord with the recommendations by the Committee for Proprietary Medicinal Products (CPMP) 482/99.

Null hypothesis superiority:

• No difference between test treatment and reference treatment

Non-inferiority clinical studies aim to demonstrate that the test treatment is no worse than the reference by more than a pre-specified small amount.

Null hypothesis non-inferiority:

• Test treatment is inferior to the reference by Δ or more

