5.1 Sample Size

A total of 130 subjects affected by *Acanthamoeba* keratitis will be assigned to one of the above two treatment groups in a ratio of 1:1.

The protocol states, in section 7.6:

"From the results of the sponsor's observational, case series retrospective study 038/SI, a CRR_12 of 67% for the conventional combination therapy of PHMB 0.02% and propamidine 0.1% is expected. This figure is in the range of cure rates described in the literature. If the true difference in CRR_12 is 0.20 (Δ) (or more) in favour of PHMB monotherapy (0.08% PHMB), a total sample size of 116 subjects (allowing for 10% loss to follow-up) should give the study at least 80% power to detect superiority, with 2-sided alpha=0.10 (or equivalently 1-sided alpha=0.05).

LINK Medical Study ID: PSR012

Assuming a prevalence of late stage disease, and worse outcomes, in 38% of subjects, the expected CRR_12 in the control group will be reduced from 67% to 63%. To account for the inclusion of this group, the sample size has been adjusted to 130 subjects (allowing for 10% loss to follow-up, i.e. 116 evaluable subjects).

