7.1.1 Presentation of Results

All results will be presented for each visit by treatment group and in total, unless stated otherwise. It should be clearly stated which unit applies to each presented variable.

Continuous data will be summarised using descriptive statistics, and the following parameters will be reported:

- number of subjects with evaluable observations and missing observations
- arithmetic mean and change from baseline with standard deviations

LINK Medical Study ID: PSR012

- median
- first and third quartiles
- minimum and maximum

Categorical data will be presented using absolute frequency and percentage. When the absolute frequency is zero, the percentage will not be presented. Unless stated otherwise, the denominator for percentage calculations will be the total number of subjects in the applicable analysis set, including subjects with missing data. For variables with missing values, the number and percentage of subjects with missing values will be presented.

Significance tests will be two-sided and performed at the 5% significance level, unless stated otherwise. When reporting the results of significance tests, p-values will be presented.

All confidence intervals (CIs) presented will be two-sided with a nominal confidence level of 95%, unless stated otherwise.

Data will be presented using an appropriate number of decimal places, to ensure that undue precision is not implied (e.g. the number of decimals should not exceed the accuracy of the measuring instrument). Raw data will be presented with the same number of decimals as collected, and derived data with an appropriate number of decimals based on general practice, mathematical rationale or scientific rationale.

Minimum and maximum values will be presented with the same number of decimals as the analysed variable and the other descriptive statistics will be presented with one decimal more. Percentages and proportions will be presented with one decimal. Odds ratios and hazard ratios will be presented with 3 decimals, and small and large values will be presented as '<0.001' and '>999.999' respectively. CI bounds will be presented with the same number of decimals as the corresponding point estimate, and p-values will be presented with 4 decimals or as '<0.001'.

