7.1.7 Multiplicity

Three hypotheses are specified in the Protocol, one primary and two secondary hypotheses. Time-to-resolution using the visit day at which resolution was first seen, will be considered statistically significant if the sum of the p-value for the primary variable and the p-value from the time-to-resolution analysis is less than the specified overall significant level. The use of a non-inferiority alternative if the difference alternative should not be obtained, does not affect the overall p-value level of the primary hypothesis.

Hypotheses tested for other secondary variables will all be analysed using significance elves of 0.05.

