7.9.1 Primary Efficacy Variable

The main endpoint disease resolution 12 months after baseline will be assessed at each visit up to study day 365.

Clinical resolution 12 months after baseline for a patient is defined as:

The percentage of subjects cured 30 days after discontinuing all study therapies, within 12 months of randomization. A clinical resolution classification requires a Yes response to the eCRF variable CRYN question: "Was clinical resolution obtained?" at one of the study visits from day 1 up to study day 365 in combination with a response *No* to the eCRF variable RELAPYN question "Did the subject experience relapse since the last visit?" at the pursuing visits, up to the last recording of this information. There should be no relapses after (the last) clinical resolution classification. Discontinued subjects will be regarded as not cured.

For patients defined as fulfilling disease resolution within 12 months, the date of the visit at which annotated CRYN is first answered with a Yes will be used as the date of resolution. The time-to-cure secondary variable will be the number of days from randomisation to the visit where resolution was recorded.

Since it is also possible to test for non-inferiority if the superiority hypothesis is not met, additional conditions are specified (see list below) to meet the strict requirements of a non-inferiority study, making it feasible to test for non-inferiority using the results from the superiority analysis, without a further separate analysis. The 90% CI for the difference between the treatments obtained from the superiority analysis gives the necessary information. Position of the lower end of the CI relative to a pre-defined agreed 0.20 non-inferiority margin (Δ) provides the key information for making decisions (conclusions) about non-inferiority.

PHMB has received the orphan drug designation. The use of 90% CI for the difference between the two treatments is to provide a 95% lower CI limit for non-inferiority.

The additional conditions specified to make testing for non-inferiority feasible are the following:

- Pre-defined non-inferiority margin (Δ =0.20) based on both clinical and statistical considerations, i.e., chosen on the basis of external information and not chosen to fit the data.
- Analysis of the FAS and the PPAS, giving similar results with respect to p-values and CIs for the
 efficacy measure at issue.

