- Study design and implementation directed at minimizing deviation from protocol (a particularly important source of bias in non-inferiority studies), e.g. special care to minimize violations of: entry criteria; non-compliance; withdrawals; loss; missing data; etc. This should help ensure the second bullet point.
- Evidence that the standard treatment is showing its usual (expected) level of efficacy.

These specifications are in accord with the recommendations by the Committee for Proprietary Medicinal Products, in document *Points to consider on switching between superiority and non-inferiority* (CPMP) 482/99. The recommendation regarding similar results with respect to p-values and CIs is founded on that the FAS "is generally not conservative and its role should be considered very carefully" in non-inferiority trials.

Null hypothesis difference:

No difference between test treatment and reference treatment

Non-inferiority clinical studies aim to demonstrate that the test treatment is no worse than the reference by more than a pre-specified small amount.

Null hypothesis non-inferiority:

• Test treatment is inferior to the reference by Δ or more

CRR_12 will be analysed using a general linear model (GLM) approach with treatment as factor to estimate the difference between success rates for the treatments, and test for difference between treatments. This will be the primary test of efficacy. The new treatment will be declared as non-inferior to the 0.02% PHMB + 0.1% propamidine combination therapy, if the lower limit of the 95% CI satisfies the requirement of a non-inferiority margin of Δ =0.20. The effects of covariate variables on the success rate will also be assessed using the GLM model with treatment, age and sex as explanatory variables. Further explorative analyses will be conducted by adding other, selected variables such as steroid use before treatment start, to the GLM model.

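### SAP 7.9.1 does not fix one significance level and sidedness for CRR_12: a 90% interval and alpha 0.10 stand beside an unqualified 95% interval and a two-sided 5% default

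*SAP*

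**What the plan says.** **Places that point to two-sided 0.10 and a 90% interval**

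- SAP 5.1, quoting protocol 7.6, sizes the trial for "80% power to detect superiority, with 2-sided alpha=0.10 (or equivalently 1-sided alpha=0.05").
- Protocol 7.4.1 reads non-inferiority from an interval it names as "The 90% confidence interval for the difference between the treatments". SAP 7.9.1 repeats this: "The 90% CI for the difference between the treatments obtained from the superiority analysis gives the necessary information".
- SAP 7.9.1 then explains the choice: "The use of 90% CI for the difference between the two treatments is to provide a 95% lower CI limit for non-inferiority".
- SAP 7.11 announces no change to the planned analyses.

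**Places that point to two-sided 5% and 95%, or give no level**

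- The declaration sentence, later in SAP 7.9.1, calls the new treatment non-inferior "if the lower limit of the 95% CI satisfies the requirement of a non-inferiority margin" of 0.20. It does not say one-sided or two-sided.
- SAP 7.1.1 sets the defaults: "Significance tests will be two-sided and performed at the 5% significance level, unless stated otherwise", and "All confidence intervals (CIs) presented will be two-sided with a nominal confidence level of 95%, unless stated otherwise".
- SAP 7.9.1 names the linear-model comparison of success rates as the primary efficacy test but gives it no alpha.
- SAP 7.1.7 calls time-to-resolution significant if the sum of its p-value and the primary p-value "is less than the specified overall significant level". No number is attached.

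**The concern.** This is the decision rule for the only primary endpoint. The sentence that explains the 90% interval shows what was probably meant, but it speaks of non-inferiority only, and the sentence that declares success does not repeat it. Read with the defaults in 7.1.1, the declaration sentence requires the lower end of a two-sided 95% interval, which is one-sided error 0.025 instead of 0.05. The superiority test, read the same way, runs at two-sided 5%, although the sample size was derived at 10%.

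Two competent analysts could follow the SAP and reach different conclusions on borderline data. If the level is settled only after the code is broken, a positive result that holds at 90% but not at 95% can be challenged from the SAP's own text.

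**Working it through.** **Inputs.** From SAP 5.1: control CRR_12 63% (67% before the late-stage adjustment), true difference 0.20, 1:1 allocation, 130 randomised, 116 evaluable (58 per arm), 80% power, two-sided alpha 0.10. From SAP 7.9.1: margin 0.20. Assumption for non-inferiority: equal true rates in the two arms, because the documents state no non-inferiority power.

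**1. Reproduce the plan's sample size.** Unpooled two-proportion formula: n per arm = (z₁₋α/₂ + z₀.₈₀)² × [p₀(1−p₀) + p₁(1−p₁)] / 0.20².

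- 67% vs 87%, alpha 0.10: (1.645 + 0.842)² × (0.2211 + 0.1131) / 0.04 = 51.7, so 52 per arm and 104 evaluable. 104/0.9 = 115.6, so 116 randomised, as stated.
- 63% vs 83%, alpha 0.10: (1.645 + 0.842)² × (0.2331 + 0.1411) / 0.04 = 57.8, so 58 per arm and 116 evaluable. 116/0.9 = 128.9, so 129 against the stated 130.

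The plan's figures are therefore right at two-sided 0.10.

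**2. Superiority at the two levels (63% vs 83%, 58 per arm).** SE = √[(0.2331 + 0.1411)/58] = 0.0803. Power = Φ(0.20/0.0803 − z₁₋α/₂).

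| Level | Power | Evaluable for 80% power |
|---|---|---|
| two-sided 0.10 | 80.1% | 116 (58 per arm) |
| two-sided 0.05 | 70.2% | 148 (74 per arm), about 165 randomised |

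A pooled-variance formula gives 78.9% and 68.4%.

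**3. Non-inferiority at the two levels (58 per arm).** At 63% in both arms, SE = √(2 × 0.63 × 0.37/58) = 0.0897. Power = Φ(0.20/0.0897 − z).

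| True rate in both arms | 90% interval (z = 1.645) | two-sided 95% interval (z = 1.960) |
|---|---|---|
| 63% | 72.1% | 60.7% |
| 67% | 74.1% | 63.0% |

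**4. Boundary cases.** These use control 37/58 (63.8%), the standard error of the linear model named in 7.9.1, and t quantiles on 114 df (1.658 and 1.981).

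| Test cures | Difference | Lower limit, 90% | Lower limit, 95% | Changes |
|---|---|---|---|---|
| 46/58 | +15.5 points | +1.7 | −1.0 | superiority claimed or not |
| 35/58 | −3.4 points | −18.5 | −21.4 | non-inferiority claimed or not |

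Superiority needs 46 test cures at 90% and 47 at 95%. Non-inferiority needs 35 and 36. With simple unpooled Wald limits the superiority thresholds are 45 and 47, and the non-inferiority thresholds stay at 35 and 36.

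**5. How often the reading matters.** I enumerated all outcomes with 58 per arm, used the limits of step 4, and classed each as superior, non-inferior or neither. The enumeration gives superiority power of 79.5% and 69.5% at 63% vs 83%, and non-inferiority power of 70.4% and 60.2% at equal 63%, close to steps 2 and 3.

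| True rates (test vs control) | Trials in which the two readings disagree |
|---|---|
| 83% vs 63% | 10.2 of 100 |
| 63% vs 63% | 12.9 of 100 |
| 87% vs 67% | 8.7 of 100 |
| 67% vs 67% | 13.7 of 100 |

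At equal 63%, about 10.2 of the 12.9 are lost non-inferiority claims. The other 2.7 are false superiority claims that the stricter level removes.

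**6. Multiplicity rule in 7.1.7.** Suppose the primary p is 0.03 and the time-to-resolution p is 0.04. The sum, 0.07, is significant if the overall level is 0.10 and not significant if it is 0.05.

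**The case against.** The strongest reply is that the documents already show one intent.

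- **Non-inferiority.** SAP 7.9.1 says the 90% interval serves to give a 95% lower limit. The later reference to a 95% interval is then most naturally the same one-sided limit, loosely worded.
- **Superiority.** The 90% interval is said to come from the superiority analysis, which corresponds to a two-sided 0.10 test, and SAP 5.1 states alpha 0.10 outright.
- **Defaults.** Those in 7.1.1 yield wherever something else is stated. The SAP introduction wants changes to principal features to go into a protocol amendment as well, and 7.11 declares no change to the planned analyses.
- **Multiplicity.** Section 7.1.7 gives 0.05 to the other secondary variables, which suggests a different level for the primary pair.

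Most of this stands as evidence of intent, and I accept 0.10/90% as the probable meaning. It does not remove the conflict. The sentence that declares non-inferiority is unqualified, and the SAP's own default makes an unqualified 95% interval two-sided. Alpha 0.10 appears only in sample-size text quoted from the protocol, so whether it overrides the default for the primary test has to be argued. The number in 7.1.7 is absent on any reading.

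It is also fair to say that the verdict-change rates treat the interval as the whole rule. SAP 7.9.1 further asks for agreement between the full and per-protocol sets and for evidence of the expected control efficacy.

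**Conclusion.** The concern holds and should be fixed before unblinding. The sample size is not in error: its power of about 80% is right at two-sided 0.10. The defect is that the analysis text does not bind the primary tests to that level and, applied literally, tests them at another.

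On the literal 5%/95% reading, superiority power is about 70% and non-inferiority power about 61%, and the conclusion changes in roughly one trial in ten. These figures assume 58 evaluable subjects per arm and a 63% control rate. The non-inferiority figure also assumes equal true rates, and the verdict-change rates consider the interval alone. The 46/58 and 35/58 examples are boundary cases. They show that a single cure can decide the outcome, not that it usually will.

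**What to change.** If 0.10/90% is intended, as the documents suggest:

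1. In the declaration sentence of SAP 7.9.1, name the interval as *the lower limit of the two-sided 90% CI (equivalently the one-sided 95% lower limit)*.
2. In the same section add: *Superiority for CRR_12 is tested at two-sided alpha 0.10; the defaults in 7.1.1 do not apply to CRR_12.*
3. In SAP 7.1.7, give 0.10 as the overall level.

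If the sponsor instead intends two-sided 5% and 95%, say so in all these places and restate superiority power as about 70% in protocol 7.6 and SAP 5.1. Because this would change the level in the protocol, the SAP introduction calls for a protocol amendment as well.

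The first option costs three sentences, with no new data and no change in sample size. The second costs a less favourable stated power.

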7.9.2 Justification for choice of the non-inferiority margin

On statistical grounds:

Our pre-defined non-inferiority margin of Δ =0.20 is based on previous studies (historical data), i.e., the study referred to in the protocol showing 1/20 cured without treatment being the only data available that can be used to estimate the cure with placebo, and the results of the reference (standard) treatment from the SIFI / Moorfields observational studies, adjusted for inclusion of advanced disease cases in the study. The table below demonstrates the statistical grounds for the choice of Δ . The chosen Δ of 0.20 satisfies the condition that "the test treatment is expected to retain at least 50% of the standard treatment effect over placebo, in order to be considered as noninferior".

Table 1: Selection of Non-Inferiority Margin (Δ) based on statistical issues

		Proportion	
Α	Cured with no treatment: Historic Data	0.05	
В	Cured with Standard Treatment: SIFI Study Data	0.67	
Ва	B adjusted for inclusion of stage-3 cases (63/100)	0.63	
Ba (lower)	Lower 95% CI bound for Ba (Binomial exact)	0.53	
M1	${f Ba}$ (lower) – ${f A}$: the standard treatment effect over placebo	0.48	
Δ	Non-inferiority margin	0.20	
Proportion of M1 retained by the Test treatment; $(M1 - \Delta)/M1$ 58%			
The Test Treatment retains well over 50% or the Standard treatment effect over placebo			

On clinical grounds:

The Sponsor proposes as clinically acceptable a non-inferiority margin of 0.20: this is within the accepted level for a study of this kind in view of the following:

- A poor response to therapy is common in this disease. Disease progression is slow in this disease (over weeks and months) and clinicians have to assess the effect of treatments every 1-2 weeks, in cases not progressing well, and modify therapies to optimize outcomes. Because of the disease chronicity the use of an ineffective treatment for these periods results in a delayed response, but no serious short term morbidity. The study results may indicate non-inferiority, when at worst the true difference in proportion 'cured' (Combined PHMB alone) is 0.20. The most likely impact of such a finding on clinical practice will be to encourage the use of PHMB monotherapy as a first line treatment.
- However, if PHMB monotherapy fails in clinical practice during the early stages of treatment, which is
 to be expected in some subjects, the clinician is unlikely to abandon the good clinical practice of
 monitoring the disease progress closely and adding other antiamoebics to the therapy when
 necessary.
- At worst, the impact of the study finding might result in a little delay (matter of days) in starting a combined treatment in some patients, whilst giving a chance for the biguanide mono-therapy to act.

LINK Medical Study ID: **PSR012**

> This scenario is unlikely to result in blindness or serious morbidity. It may cause some delay in the clinical resolution.

By contrast, the possibility that the true difference may be much smaller than 0.2, or even in favour of PHMB monotherapy, will have important beneficial consequences for patients and ophthalmic services.

7.9.3 Secondary Efficacy Variables¹

Time-to-cure comparison between the treatment groups is specified as efficacy hypothesis and will be subjected to formal statistical testing. Other analyses of secondary efficacy variables will be done on a hypothesis-generating basis, i.e. no p-value adjustments will be conducted, and conclusions regarding the analysis results will be commented on such a basis.

Time-to-cure

The aim of the hypothesis test is to show that the time is less among the subjects receiving PHBM 0.08% monotherapy compared to the comparator. Patients will either be classified as Cured at some point of time while in the study or leave the study without being classified as Cured. As a secondary efficacy variable, timeto-cure (clinical resolution) will be analysed. The Cox Proportional Hazards regression (subject to validity of the 'proportional hazards' assumption) and Kaplan-Meier survival plots. If the proportional hazard assumption is not fulfilled a logrank test will be performed. Not all patients may have information regarding when they were cured, e.g. due to death before being cured, or completed the study without being cured. Both the Cox Proportional Hazards regression and the Kaplan-Meier plot uses the censoring timepoint in their calculations. The censoring timepoint will be defined based on the timepoint of the last observation when cure status was assessed. The null hypothesis is that the two treatment arms have equal hazard functions. Relevant data will be presented at the Clean file meeting for discussion and acceptance.

BCVA

The VAMS states that: "Depending on the problem, this notation can be most useful when analysing or graphically plotting visual acuity scores because equal linear steps on the LogMAR scale represent equal ratios in the standard size sequence." Hence, BCVA will be presented and analysed using LogMAR values, where

$$LogMAR = \log \left(\frac{ORRES_{BCA2}}{ORRES_{BCA1}} \right),$$

where ORRES BCA1 and ORRES_BCA2 are the annotated values from the BCVA test. These values are positive number with up to one decimal value. ORRES BCA1 values recorded in the eCRF, the distance from the subject to the chart, varies at least from 0.6 to 10 metres. Even if different scales are used (Decimal, US, 6m), the LogMAR is not affected since the ratio will be the same, therefore no converting to unified units is needed². BCV A, as a secondary efficacy variable, will be analysed. ANCOVA will be used with treatment and the Baseline value of LogMAR as predictors. Refraction at Baseline may also be used as a predictor.

Drug compliance

Drug compliance is recorded as Yes or No answer to the question "Was the study drug administration compliant with the protocol?", annotated as PROTCOMYN. Drug compliance will be analysed with a logistic regression model and model-based estimates of the difference between treatments, odds ratio with corresponding CIs and p-values will be provided. Covariate variables such as treatment, age and sex will be included. Any available information regarding drug use will also be presented, such as number of vials returned.

EQ-5D-5L3 & EQ VAS, at all visits

EQ-5D-5L consists of 5 dimensions, Mobility, Self-care, Usual activities, Pain/discomfort, and Anxiety/depression, each answered with one of five different answers:

Mobility:

I have No problems/Slight problems/Moderate problems/Severe problems in walking about/I am unable to walk about

³ One subject, aged 15 years, used the EQ-5D-Y version. At site 31, Silesia, all subjects at one or more visits used the EQ-5D-3L version

Transaction 09222115557449620377 Signed CE, VP, MS

¹ For safety variables, see Section 7.10.2

² RR.2 Reference Tables For Equivalent Visual Acuity Notations

LINK Medical Study ID: PSR012

Self-care:

I have No problems/Slight problems/Moderate problems/Severe problems in washing or dressing myself/I am unable to wash or dress myself

Usual activities (e.g. work, study, housework, family or leisure activities):

I have No problems/Slight problems/Moderate problems/Severe problems doing my usual activities/I am unable to do my usual activities

Pain/discomfort:

I have No pain or discomfort/Slight pain or discomfort /Moderate pain or discomfort /Severe pain or discomfort/I have extreme pain or discomfort

Anxiety/depression:

I am not/slightly/moderately/severely/extremely anxious or depressed.

The EQ-5D will be summarised for each dimension. A table presenting the number of subjects reporting a problem, i.e. a score higher than 1, will also be presented. A repeated measures ANCOVA for each dimension will be conducted using treatment and the baseline value as predictors.

The EQ VAS score, annotated as ORRES_EQ5D0206, is being recorded at all visits, including Baseline. Integer values range from 0 to 100. A repeated measures ANCOVA will be used to compare potential differences in trends over the treatment period using treatment and the Baseline VAS value as predictors.

Slit-Lamp Examination, at all visits

Below can be seen the different efficacy variables based on the Slit lamp examination. These will be presented in tables, as can be seen in the Data Display Plan (DDP). Some of these variables will only be recorded in *Specify* types of eCRF fields and will be converted to a *Yes/No* variable before tabulation and possible analysis.

Corneal scarring

Corneal scarring is being assessed as *Present* or *Absent*, using the slit lamp biomicroscopy, and is annotated as SLECOSCAR. This is being performed by the examining ophthalmologist, using a slit lamp biomicroscope. Detailed information about the procedure is provided in the Study Operation Manual. As a stated secondary variable, corneal scarring at EoT will be analysed with logistic regression using treatment group and corneal scarring at baseline as predictors.

Ulceration severity

Ulceration severity is being assessed as *Present* or *Absent* by the examining ophthalmologist using the slit lamp biomicroscope and is annotated as SLECOUL. As a stated secondary variable, ulceration severity will be analysed with logistic regression using treatment group and ulceration severity at Baseline as predictors.

Conjunctiva

Erythema grade SLECER (using grades 0, 1, 2, 3)

Oedema grade SLECED (using grades 0, 1, 2, 3, 4)

Discharge SLECOND (Present, Absent)

Papillae SLECONP (Present, Absent)

Follicles SLECONF (Present, Absent)

Limbitis

Scleritis

Corneal Abnormalities⁴

Dendritiform epithelial lesions

Perineural infiltrates

Corneal epithelial defects (punctate erosions),

Corneal epithelial ulcer (confluent erosions)

Corneal epithelial defects SLECOED (Present, Absent)

Corneal ulceration SLECOUL (Present, Absent)

Corneal epithelial opacity SLECOEO (Present, Absent)

Corneal stromal opacity SLECOSO (Present, Absent)

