1. INTRODUCTION

The Orphan Drug for *Acanthamoeba* keratitis (ODAK) is a project aiming to investigate the potential of polyhexamethylene biguanide (PHMB) as a safe and effective drug for the treatment of the rare eye disease *Acanthamoeba* keratitis. This debilitating infectious disease is caused by a commonly occurring protozoan and in the absence of treatment can result in blindness. There are currently no approved drugs to treat this disease.

PHMB has received the orphan drug designation (EU/3/07/498) according to EC regulations 141/2000.

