7.4.2. Secondary Efficacy Variable

Which test to be used in the analyses of secondary efficacy variables depends on the type of variable, e.g., logistic regression for binary variables, proportional odds model for an ordinary scaled variable, analysis of variance (ANOVA) or covariance (ANCOVA) for continuous variables as appropriate. If the underlying assumptions are not fulfilled, data transformation or non-parametric test will be performed. For comparison of proportions, Chi square tests, Fisher's exact test, or Mantel-Haenszel procedures, as appropriate, will be considered. For continuous variables, the Wilcoxon rank-sum test or rank ANOVA/ANCOVA will be used. The STATA or SAS statistical software will be used for the analysis.

EQ-5D and VFQ25 will be evaluated according to their respective analysis protocols.

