7.1.5 Handling of Missing Data

Sensitivity analyses performed for a single variable are described in detail in the corresponding section below.

Data listings will include the observed values. For derived variables, values based on imputed data will be presented in listings.

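### The LogMAR analysis of visual acuity has no rule for an eye that reads no letter or has been removed, so such eyes leave the comparison because of their vision.

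*SAP*

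**What the plan says.** BCVA heads the list of secondary efficacy variables in protocol 6.4 and SAP 3.3.1. SAP 7.9.3 fixes the scale: "BCVA will be presented and analysed using LogMAR values, where" LogMAR is the log of ORRES_BCA2 over ORRES_BCA1. On the two fields it says: "These values are positive number with up to one decimal value". ORRES_BCA1 is the testing distance: "ORRES BCA1 values recorded in the eCRF, the distance from the subject to the chart, varies at least from 0.6 to 10 metres". The model follows: "ANCOVA will be used with treatment and the Baseline value of LogMAR as predictors".

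SAP 6.2.1 lists only numeric notations (Snellen, decimal, visual angle, LogMAR). The general section on missing data, SAP 7.1.5, defers to the individual variables: "Sensitivity analyses performed for a single variable are described in detail in the corresponding section below". The BCVA text in SAP 7.9.3 contains no such analysis and no imputation rule. The Schedule of Assessments plans BCVA only at Day 0 and at end of study. Both documents refer to the Study Operation Manual, which is not available here, for how acuity is measured.

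**The concern.** An eye limited to hand movements or light perception, an eye with no light perception, and an eye that has been removed all lack a chart ratio. With no substitute value or rank, they cannot enter an ANCOVA on observed LogMAR.

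Such eyes are foreseeable. Protocol 4.1 accepts a fixed dilated pupil and mature cataract at entry. The sample size sections assume late-stage disease in 38% of subjects. SAP 7.10.9 plans to tabulate evisceration and enucleation. Footnote 4 to the Schedule of Assessments gives treatment failures an end-of-study visit, so the worst eyes are due a BCVA measurement. The SAP does score complete blindness in the VFQ-25, where response 6 of item 2 is recoded to 0, but the acuity analysis has no counterpart.

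What is at stake is the comparison of visual outcome. If one arm leaves more eyes off the chart at the end, more of its worst results disappear and its mean looks better than it should.

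**Working it through.** The plan gives no BCVA sample size, standard deviation or target difference, so there is no figure to reproduce. Three checks apply.

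1. **Where the formula fails.** LogMAR = log10(BCA2 / BCA1). If BCA1 is zero the ratio is a division by zero; if BCA2 is zero the log is undefined; if either is blank there is no ratio. The ANCOVA needs the result twice, as outcome and as covariate, so a gap at either visit removes the subject. With BCVA planned only at those two visits, there is no scheduled intermediate value to use instead.

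2. **How far close testing extends the scale.** The SAP reports distances down to 0.6 m. Assume a letter of 60 m size (the documents do not give chart sizes). At 6 m, log10(60/6) = 1.0. At 0.6 m, log10(60/0.6) = 2.0. Very poor acuity can therefore be recorded, and the affected group shrinks to eyes that read nothing even close up. Those eyes still have no value.

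3. **What dropping them could hide.** All inputs here are assumptions:
   - readable eyes average LogMAR 0.3 in both arms;
   - off-chart eyes are valued at 2.0 to 3.0;
   - the off-chart share at the outcome visit is 5% in the better arm and 5%, 10% or 15% in the worse arm;
   - no eyes are lost at baseline.

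   Mean in an arm = 0.3 × (1 − q) + v × q, where q is the off-chart share and v the assigned value. The hidden difference between arms is (q_worse − q_better) × (v − 0.3). If off-chart eyes are dropped, the observed difference is 0.00 in every row.

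| Off-chart share, worse v better arm | v = 2.0 | v = 3.0 |
|---|---|---|
| 5% v 5% | 0 × 1.7 = 0 | 0 × 2.7 = 0 |
| 10% v 5% | 0.05 × 1.7 = 0.085 | 0.05 × 2.7 = 0.135 |
| 15% v 5% | 0.10 × 1.7 = 0.17 | 0.10 × 2.7 = 0.27 |

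For scale, SAP 5.1 plans 116 evaluable subjects, or 58 per arm. Then 5% is 2.9 eyes and 10% is 5.8, so the second row rests on about three extra eyes in one arm.

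**The case against.** The strongest reply is that the SAP is silent and does not order exclusion. A reader might infer that blind eyes are excluded by design. The documents do not support that, because the Study Operation Manual or the eCRF conventions may assign a number. This stands: the supportable statement is that the SAP gives no rule.

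The evidence that such eyes will occur can also be pressed too far. The protocol introduction says the disease "in the absence of treatment can result in blindness", but both arms are treated, and protocol 4.2 excludes subjects needing urgent surgery. For treatment failures the final assessment falls at trial exit, so an eye removed later would keep its value. These facts lower the expected number without making it zero.

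A reader might infer from the one-decimal fields that low decimal acuities are rounded to 0.1 or to zero, especially as the SAP says "the LogMAR is not affected since the ratio will be the same, therefore no converting to unified units is needed". The text does not support this. It states no rounding rule, requires positive values and stores a ratio; a decimal acuity of 0.05 can be held exactly as 1 over 20.

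A reader might also infer that the bias must run toward no difference. Loss at the outcome visit does flatter the worse arm. But an eye off-chart at baseline is also lost, even if it recovers, and that can act in either direction.

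Finally, existing provisions cover part of the gap. SAP 7.1.1 reports missing counts by arm and visit, and surgery is tabulated separately. A missing count, however, does not separate a blind eye from a skipped test. Protocol 7.4.2 has a fallback: "For continuous variables, the Wilcoxon rank-sum test or rank ANOVA/ANCOVA will be used". But a rank method still needs a rank for each eye, and SAP 7.11 leaves the choice of an alternative to the analysis stage.

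**Conclusion.** The gap is real and narrow. As written, an eye that reads no letter at any distance, or that has been removed, has no LogMAR and leaves the BCVA model for a reason tied to the outcome being compared. The comparison can therefore be biased. The net direction is uncertain because losses at baseline and at outcome need not act the same way.

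The documents do not let the size be estimated. Under the stated assumptions, 10% against 5% off-chart hides 0.085 to 0.135 LogMAR, 15% against 5% hides 0.17 to 0.27, and equal rates hide nothing. The conclusion assumes that no convention outside the protocol and SAP already assigns these eyes a value.

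A reader should not carry this over to the trial's main conclusion. CRR_12 does not use BCVA, and SAP 7.9.3 treats secondary efficacy variables other than time-to-cure as hypothesis-generating. The point is still worth correcting, because a rule set before unmasking costs little and the planned fallbacks do not supply one.

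**What to change.** Before unmasking, add to the BCVA text of SAP 7.9.3:

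- **A rule for both visits.** Keep these eyes in the analysis at baseline and end of study, from least to most severe: counting fingers (if not recorded as a ratio), hand movements, light perception, no light perception, eye removed. Either use that fixed worst order or assign pre-specified LogMAR values that respect it.
- **A sensitivity analysis.** Run a rank ANCOVA, which protocol 7.4.2 already allows, beside the LogMAR ANCOVA. There is no need for it to replace the planned model.
- **A count.** Report the number of such eyes per arm and visit, separately from tests not done.

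If the Study Operation Manual already assigns values, citing them in SAP 7.9.3 supplies the rule. No change to how acuity is entered is needed.

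The cost is a paragraph of SAP text and a data query for subjects with missing numeric acuity. The downside is that the result will depend partly on the assigned values or ranks, and the rank contrast cannot be read as a mean LogMAR difference.
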